#### **12.5.2. Definition of a Serious Adverse Event**

An SAE is any AE occurring at any dose that results in any of the following outcomes:

- Death  
“Death” is an outcome and is NOT the AE. In the event of death, the cause of death should be recorded as the AE. The only exception is “sudden death” when the cause is unknown.
- Is a life-threatening experience  
Life-threatening AEs include any adverse drug experience, which, in the view of the investigator, places the subject at immediate risk of death from the reaction as it occurs. It

does not include a reaction that, had it occurred in a more serious form, might have caused death.

- Requires inpatient hospitalization or prolongation of existing hospitalization
- Results in a persistent or significant disability/incapacity  
Disability is defined as a substantial disruption in a person's ability to conduct normal life functions.
- Results in a congenital anomaly/birth defect
- Additionally, important medical events that may not result in death, be life threatening, or require hospitalization may be considered an SAE when, based upon appropriate medical judgment, they may jeopardize the subject and may require medical or surgical intervention to prevent one of the outcomes listed previously (e.g., an allergic bronchospasm requiring intensive treatment in an emergency room or at home).

### **12.5.3. Adverse Event Reporting**

[figure not shown]
Adverse events will be collected from the time of study drug administration through the last day of the subject's participation in the study. Follow-up of AEs must be conducted in accordance with the investigative site's normal practice.

All AEs must be documented, evaluated, and reported in the source documents and electronic case report forms (eCRFs), and include the following information: duration (start and stop dates or if continuing at final visit), severity, relationship to study drug, action(s) taken, outcome, and whether it constitutes a serious adverse event (SAE). Diagnoses (rather than symptoms) should be recorded wherever possible. To avoid vague, ambiguous, or colloquial expressions, all AEs should be recorded in standard medical terminology rather than in the subject's own words. Symptoms related to lack of efficacy (in the investigator's opinion) will not be recorded as AEs unless there is a clinically significant safety concern (e.g., serious adverse event).

Subjects should be instructed to report all potential AEs to the investigator. Subjects should also be queried in a non-leading manner, without specific prompting (e.g., "How are you feeling?") about all potential AEs. The site study staff should assess emerging symptoms of dissociative reaction similar to those caused by NMDA antagonists, including memory impairment, disturbance in time, body or environmental perception, stilted speech, emotional withdrawal, impaired coordination, motor retardation, bizarre reasoning or illusory experiences in any sensory perception, or confused state; such symptoms may be captured as AEs.

### **12.5.4. Serious Adverse Event Reporting**

Serious adverse event (SAE) reporting will begin from the time of informed consent and will end 30 days after the last dose of study drug. SAEs must be reported to the sponsor or designee using the provided form either by email or fax to the following address or telephone number, respectively:

All SAEs that result in death or are life threatening, regardless of causal relationship, must be reported to the sponsor or designee within 24 hours of the site's knowledge of the event. A copy of the initial SAE report must be received within one (1) business day.

All other SAEs or other events reportable to FDA and/or institutional review board (IRB) will be forwarded to the sponsor or designee within one (1) business day.

The SAE report should provide as much of the required information as is available at the time. The following minimum information is required for reporting an SAE: subject identification, reporting source, and event outcome. Supplemental information may be transmitted using a follow-up report and should not delay the initial report. Aptinyx (or its authorized representative) may contact the investigational site to solicit additional information or to follow-up on the event.

If there is any doubt whether the information constitutes an SAE, the information will be treated as an SAE for the purposes of this protocol.

All relevant documentation pertaining to an SAE (additional laboratory tests, consultation reports, discharge summaries, postmortem reports, etc.) will be provided to the sponsor or designee in a timely manner. Serious AEs will be followed until resolution or return to baseline (when worsening of a pre-existing condition is reported). If an SAE does not return to baseline but reaches a stable situation that is not expected to change, this should be documented on the SAE form.

#### **12.5.5. Relationship to Study Drug**

For each reported AE/SAE, the investigator must assess the relationship to study drug using the following categories:

##### **Unrelated**

- Does not follow a known response pattern to the suspect study drug (if response pattern is previously known).
- Can clearly be explained by the known characteristics of the subject's clinical state or other modes of therapy administered to the subject.

##### **Unlikely Related**

- The temporal sequence from dosing of the study drug suggests that a relationship is unlikely.
- Follows a response pattern that is unlike that of the suspect study drug (if response pattern is previously known).
- Could be reasonably explained by the subject's clinical state or other modes of therapy administered to the subject.

##### **Possibly Related**

- Follows a reasonable temporal sequence from dosing of the study drug.
- May follow a known response pattern to the suspect study drug (if response pattern is previously known).
- Could also be reasonably explained by the subject's clinical state or other modes of therapy administered to the subject.

### **Probably Related**

- Follows a reasonable temporal sequence from dosing of the study drug.
- Could not be reasonably explained by the known characteristics of the subject's clinical state or any other modes of therapy administered to the subject.
- Is confirmed by improvement on stopping or slowing dosing of the study drug, if applicable.

When an assessment is not provided, the event will be treated as Possibly Related for purposes of regulatory reporting.

### **12.5.6. Severity of Adverse Events**

All AEs must be assessed for severity, using the following general grading scale:

Mild: Transient or mild discomfort (< 48 hours); no medical intervention/therapy required.

Moderate: Mild to moderate limitation in activity – some assistance may be needed; no or minimal medical intervention/therapy required.

Severe: Marked limitation in activity – some assistance usually required; medical intervention/therapy, required hospitalization possible.

Life-threatening: Extreme limitation in activity – significant assistance required; significant medical intervention/therapy required, hospitalization or hospice care probable.

When changes in the severity of an AE occur more frequently than once a day, the maximum severity for the experience that day should be noted. If the severity category changes over a number of days, then those changes should be recorded separately (with distinct onset dates).

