## 4. Statistical Analysis and Reporting

### 4.1. Introduction

Data processing, tabulation of descriptive statistics, calculation of inferential statistics, and graphical representations will be performed primarily using SAS (release 9.4 or higher).

Continuous (quantitative) variable summaries will include the number of subjects (n) with non-missing values, mean, standard deviation (SD) (or standard error (SE) if appropriate), median, minimum, and maximum. Confidence intervals (CIs) will be added if appropriate.

Categorical (qualitative) variable summaries will be based on frequencies and percentages.

Unless stated otherwise, efficacy data for endpoints included in mixed effects repeated measures model (MMRM) analyses (groups [1], [2], [3], [7], [8], and [9]) will be summarized by visit and treatment group (Placebo, NYX-783 10 mg QD, NYX-783 50 mg QD) to allow for summary data treatment comparisons as per model inference.

Efficacy data for Stage 2 groups [4], [5], [6], [10], and [11] will be presented separately.

Unless stated otherwise, safety data will be summarized by Stage and treatment group (Placebo [as Placebo Only and Placebo Stage 2, separately], NYX-783 10 mg QD, NYX-783 50 mg QD); data presented by visit will be displayed based on the treatment group which applies at onset for AEs/collection date.

The minimum and maximum will be reported with the same degree of precision (i.e., the same number of decimal places) as the observed data. Measures of location (mean and median) will be reported to 1 degree of precision more than the observed data and measures of spread (SD, SE) will be reported to 2 degrees of precision more than the observed data.

Percentages will be presented to 1 decimal place, unless otherwise specified.

Unless otherwise indicated, all statistical tests will be conducted at a 0.10 significance level using one-sided tests and p-values will be reported. Corresponding 80% CIs (the interpretation of which is equivalent to a one-sided 90% CI when restricted to a single bound) will be presented.

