- Sheehan Suicidality Tracking Scale (S-STS) = The standard version of the S-STS is a 16-item scale that assesses the seriousness of suicidality phenomena on a Likert-type scale (0 to 4) ranging from 0 = “not at all” to 4 = “extremely.” The S-STS score will be derived by data-management. The S-STS accommodates a wide range of timeframes. In clinical trials, the frequently used variants are “in the past week”, “in the past month”, “since the last visit”, “lifetime look back”, and “in the past day.” In this study, during screening, "in the past month" version is used. For all the other visits "since the last visit" version of the S-STS is used.
- Subjects with high S-STS scores- Subjects with a score of 3 or 4 on any questions 2, 3, 4, 5, 6, 7, 8 or 13 in the S-STS questionnaire will be flagged.

- Placebo Non-responder = A Placebo Non-responder must satisfy the following criteria.
  - Randomized to placebo in Stage 1 of the study
  - Week 4 whose CAPS-5 total score reduction from baseline [Day 1]  $\leq 35\%$  and Week 4 CAPS-5 total score is  $\geq 26$
- Change from baseline = value at current visit – value at baseline (as defined in Section 6.1.1).
- TEAE = this is any adverse event with an onset date on or after first dose of study drug through 7 days after last dose of study drug. The Stage in which an event is considered treatment emergent will also be determined based on the relative onset timing against the first dose of Stage-specific study drug. Adverse Events with an onset during the 7 days after end of Stage 2 will be part of Stage 2.
- Duration of reported treatment period (years): For displays of TEAEs, it may be necessary to standardize rates of events due to variable treatment reporting periods. For Stage-specific reporting, durations are computed based on (the date of the last dose of study drug - the date of the first dose of Stage-specific study drug + 1).
- Treatment Related AEs= For each reported AE/SAE, the investigator assesses the relationship to study drug and categorize them into the following categories: Not Related = Unrelated and Unlikely Related, Related = Possibly Related and Probably Related). If an assessment is missing, then it will be treated as Related.
- Sexual Abuse= this is used to flag subjects who were victims of sexual abuse. If the medical history term preferred term is ‘Sexual Abuse’ or ‘Victim of Sexual Abuse’ then those subjects will be flagged as victim of sexual abuse.

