### 9.1. Adverse Events

The number, percentage and incidence rate of subjects reporting treatment emergent AEs (TEAEs), grouped by MedDRA system organ class (SOC) and preferred term (PT) (coded using MedDRA v21.1), will be tabulated by Stage, and treatment group. In the case of multiple occurrences of the same TEAE within the same subject and Stage, a subject will only be counted once for each PT or SOC. Similar methods will be used to provide summaries further reported by severity and relationship. In the summaries reporting severity and relationship to study medication the event with the maximum severity and strongest relationship will be reported, respectively. For these analyses, missing severity and relationship will be imputed as described in Section 6.1.3.2.

The frequency, percentage, and incidence rate of subjects reporting TEAEs, will be reported as described for the following summaries:

- TEAEs by SOC and PT
- TEAEs by SOC, PT, and maximum severity
- Treatment-related TEAEs by SOC and PT
- Treatment-related TEAEs by SOC, PT, and maximum severity

An overall summary of TEAEs, TEAEs leading to discontinuation of study, serious TEAEs, Severe or life-threatening TEAEs, and fatal AEs will be reported. This summary will also be reported for treatment-related TEAEs. Overall summaries for TEAEs and

treatment-related TEAEs by maximum severity will also be provided. The number of total events at each level of TEAE reporting will also be used in the calculation of incidence rate per subject-years of study participation given the specified Stage and reporting treatment period (total events/total patient-years included in the reported treatment period). In general, the duration of the reported treatment period is based on the amount of time a subject has taken the assigned drug within each Stage of reporting for a specified treatment; this is described in more detail in Section 6.1.4.

Missing and partially missing AE start and/or stop dates will be used to determine TEAE status for reporting, according to the specifications described in Section 6.1.5.

In the AE data listings, all AEs will be displayed. AEs that are not treatment-emergent will be flagged.

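### AE severity changes get their own onset dates and the SAP stages TEAEs by onset date alone, so an AE that only eases after Week 4 counts as a Stage 2 TEAE

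*Protocol*

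**What the plan says.** **Recording.** Protocol 12.5.6: "If the severity category changes over a number of days, then those changes should be recorded separately (with distinct onset dates". No direction is given. The one limit is for changes within a single day, which collapse to that day's maximum.

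**TEAE definition.** SAP 6.1.4 takes "any adverse event with an onset date on or after first dose of study drug", up to 7 days after the last dose. The stage is "determined based on the relative onset timing against the first dose of Stage-specific study drug". Neither sentence asks whether the event is new or worse.

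**Treatment group.** SAP 4.1 summarises safety by stage and treatment group, with placebo split into Placebo Only and Placebo Stage 2. It adds that "data presented by visit will be displayed based on the treatment group which applies at onset for AEs/collection date".

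**Counting.** SAP 9.1 counts a subject once per preferred term (PT) or system organ class (SOC), but only within the same stage. For the rate, the "number of total events at each level of TEAE reporting will also be used in the calculation of incidence rate", divided by patient-years.

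**The concern.** Taken separately these rules are ordinary. Together they let a change of grade act as a new onset. In a sequential parallel design that matters at Week 4, because most subjects change treatment there and the onset date decides which treatment an AE is charged to.

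The result also runs the wrong way. An AE that stays moderate through Week 4 has no new onset date and adds nothing to Stage 2. The same AE, if it improves to mild, becomes a Stage 2 TEAE.

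Safety and tolerability are part of the study's overarching goal. The AEs of interest in SAP 9.2, several of which (depression, anxiety, nightmares) can fluctuate in severity, use the same stage-based summaries.

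**Working it through.** The plan states no figure on this point, so there is nothing to reproduce. I applied the rules literally and then looked at scale.

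**Step 1. Single cases.** Stage 2 dosing starts the day after the Week 4 visit (Protocol 10.1), so on Day 29 if the visit falls on Day 28. Entries are subjects / events.

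| AE history | Stage 1 as written | Stage 2 as written | Stage 1 intended | Stage 2 intended |
|---|---|---|---|---|
| Moderate from Day 20, mild from Day 33 | 1 / 1 | 1 / 1 | 1 / 1 | 0 / 0 |
| Moderate from Day 20, unchanged past Week 4 | 1 / 1 | 0 / 0 | 1 / 1 | 0 / 0 |
| Mild, moderate, mild, all in Stage 1 | 1 / 3 | 0 / 0 | 1 / 1 | 0 / 0 |
| Mild from Day 20, moderate from Day 33 | 1 / 1 | 1 / 1 | 1 / 1 | 1 / 1 |

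The first row is the cross-stage error, and it reaches subject counts as well as events. The third row is the within-stage error, and it reaches events only. The fourth row comes out right.

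**Step 2. Is there another rule that stops this?** Protocol 12.5.1 has a worsening condition, but only for conditions present before study drug dosing, not for AEs that start in Stage 1. Protocol 14.10.1 counts a subject once per preferred term, which protects subject counts only, and SAP 9.1 narrows that to within a stage. Neither document links severity records or keeps the first onset date.

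**Step 3. How many subjects cross the boundary onto a different treatment?** Inputs: 156 subjects, 4:1:1, then 3:2:2 (Protocol 7.1, 10.2); 15% Stage 1 dropout (Protocol 14.2), assumed equal across arms.

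- Stage 1 placebo: 156 × 4/6 = 104. Active: 156 × 2/6 = 52.
- Entering Stage 2: 104 × 0.85 = 88.4 and 52 × 0.85 = 44.2, total 132.6.
- Placebo to active: 88.4 × 4/7 = 50.5. Active to placebo: 44.2.
- Changing treatment: (50.5 + 44.2) / 132.6 = 71%.

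**Step 4. Sensitivity of the Stage 2 rate.** Each re-randomised dose group has 88.4 × 2/7 = 25.3 subjects. Assuming 28 days each, exposure is 25.3 × 28/365.25 = 1.94 patient-years. Event counts below are assumptions.

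| Genuine Stage 2 events | Carried-over easing records | Rate without them | Rate as written | Ratio |
|---|---|---|---|---|
| 10 | 2 | 5.16 | 6.20 | 1.2 |
| 10 | 4 | 5.16 | 7.23 | 1.4 |
| 5 | 2 | 2.58 | 3.62 | 1.4 |
| 5 | 4 | 2.58 | 4.65 | 1.8 |

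Within a stage, the event rate is multiplied by the mean number of records per AE: 1.5 records give 1.5 times the rate, 2 give twice.

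**The case against.** **The recording rule may not create new AEs.** Protocol 12.5.6 says changes are recorded separately; it does not say that a new AE is opened. Protocol 12.5.3 asks for start and stop dates for each AE, and 12.5.8 offers an outcome category for events that are resolving. Both fit one record per AE. The eCRF layout that would settle this is not in the documents. The doubt stands, but it does not close the gap: the SAP keys on onset dates, 12.5.6 creates several for one AE, and nothing says which to use.

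**Subject counts are protected within a stage.** This stands. A reader might infer that all TEAE frequencies are multiplied. Within a stage, only total events and the rate are. SAP 6.1.4 introduces standardised rates as something that may be needed, but SAP 9.1 lists the incidence rate among the quantities to be tabulated.

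**The Stage 2 comparison of drug with placebo is not shown to be biased.** A reader might infer that the error favours or penalises the drug in Stage 2. The documents do not support that. Reading Placebo Only as subjects on placebo throughout, the Placebo Only, 10 mg and 50 mg groups in Stage 2 all come from Stage 1 placebo by re-randomisation. AEs carried over from Stage 1 are therefore balanced across them in expectation and act as added background. Former active subjects, whose drug AEs may ease on placebo, appear in the separate Placebo Stage 2 group. It is also tempting to say that an arm with more moderate or severe AEs is inflated most. That could hold for event rates, but no figure in the documents supports a size.

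**Consequence is limited.** This also stands. The trial is an exploratory proof of concept, all AEs are listed, and the study stopping rule (Protocol 13.2) rests on individual stopping criteria and unblinded review by the safety board, not on TEAE rates.

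**Conclusion.** The point holds as a defect in safety reporting. Followed as written, the plan counts an AE that began in Stage 1 and only eased as a Stage 2 TEAE, and counts each severity step as an event in the rate.

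Two displays are affected. Across stages, both subject counts and rates gain spurious Stage 2 TEAEs: background in the three re-randomised groups, and easing Stage 1 drug AEs in the Placebo Stage 2 group. Within a stage, only event totals and rates are inflated.

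The size depends on how often severity changes and how many AEs are ongoing at Week 4, and the documents give neither. The ratios of 1.2 to 1.8 above illustrate how sensitive groups of about 25 are; they are not estimates. The conclusion assumes that severity records reach the analysis dataset with separate onset dates, as Protocol 12.5.6 describes. Primary efficacy is unaffected.

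**What to change.** Amend SAP 6.1.4 and 9.1 before unblinding:

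1. Join AE records of the same subject and preferred term with contiguous dates into one episode, with the first onset date.
2. Count the episode once in the stage of first onset, at the maximum severity reached in that stage.
3. Count it once more, in Stage 2, only if its severity after the first Stage 2 dose exceeds its severity on the last day of Stage 1.
4. Apply the same rule to subject counts and to the event-rate numerator.
5. Keep every severity record in the listings.

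The cost is a few lines of SAP text and one derivation step; sites change nothing and no data are lost. The downside is that a true recurrence on contiguous dates would be merged with the earlier episode.

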### **12.5.7. Action Taken for Adverse Events**

For each reported AE, the action taken must be evaluated and recorded on the eCRF according to the following criteria:

- No action taken
- Concomitant medication taken
- Hospitalization or prolongation of hospitalization
- Discontinued study
- Non-drug therapy
- Other (specify)

The investigator must also document on the eCRF the action taken with study drug (as a result of a given AE) according to the following criteria:

- Dose not changed
- Study drug withdrawn

- Not applicable
- Unknown

#### **12.5.8. Outcome for Adverse Events**

For each reported AE, the investigator must document the outcome according to the following criteria:

- Fatal
- Not recovered/ not resolved
- Recovered/ resolved
- Recovered/ resolved with sequelae
- Recovering/ resolving
- Unknown

#### **12.5.9. Other Reportable Events**

Reports of overdose (with or without an AE), abuse, dependency, inadvertent or accidental exposure, pregnancy, and unexpected therapeutic benefit should be forwarded in the same time frame as an SAE. Overdose occurs when a subject is dosed or has taken a dose greater than the intended or scheduled dose specified by the protocol.

All pregnancies occurring during the study must be followed for information regarding the course of pregnancy, delivery, and condition of the newborn. Follow-up should be provided by the investigator to the sponsor in a timely manner. When the newborn is healthy, further follow-up is not necessary. Male subjects must inform the investigator if their partner becomes pregnant during the study. Female subjects of childbearing potential and female partners of male subjects must use an acceptable method of birth control during the participation in this study.

